6.7 Dose Modification

No dosing modifications are permitted.

6.8 Treatment after the End of the Study

The Sponsor will not provide any additional care to subjects after they leave the study because such care should not differ from what is normally expected for subjects with moderate-to-severe AD.

7.0 DISCONTINUATION OF STUDY TREATMENT AND SUBJECT DISCONTINUATION/WITHDRAWAL

7.1 Discontinuation of Study Treatment

See the SoA for data to be collected at the time of Early Termination/Treatment Discontinuation and follow-up and for any further evaluations that need to be completed.

7.1.1 Temporary Discontinuation

In the event of an AE or clinically significant laboratory abnormality, study treatment of a subject may be temporarily discontinued based on the Investigator's judgment and preferably following a discussion with the Medical Monitor in accordance with the guidelines described in this section.

If during the course of treatment, a subject experiences a new (i.e., not existing at baseline) cardiovascular or hematologic AE (including laboratory abnormalities confirmed by repeat testing), consistent with Common Terminology Criteria for Adverse Events (CTCAE) Version 5.0 [CTCAE 2017] of Grade 2 or higher, then the study drug should be temporarily discontinued for that subject. Treatment may be re-initiated if the abnormality resolves within 2 weeks of the onset of the AE.

In the event of a clinically significant laboratory abnormality, study treatment may be temporarily discontinued at the Investigator's discretion. A decision to temporarily discontinue treatment with the study drug and/or to reinstitute study treatment should be discussed with the Medical Monitor. The Investigator may suspend study treatment at any time, even without consultation with the Medical Monitor if the urgency of the situation requires immediate action and if it is determined to be in the subject's best interest. However, the Medical Monitor should be contacted as soon as possible for all cases of study drug discontinuation/interruption. Resumption of study treatment after temporary discontinuation should always be discussed with the Medical Monitor. Resumption of investigational product may occur so long as the laboratory finding has returned to Baseline or has only mild out-of-range levels less than or equal to 2 weeks from onset of the laboratory abnormality.

The information pertaining to interruption or discontinuation of study drug and the reasons for it must be recorded in the case report form (CRF).

No dose reductions or modifications will be permitted in RPT193-02.

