- If during the course of treatment, a subject experiences a new onset cardiovascular adverse event consistent with Common Terminology Criteria for Adverse Events (CTCAE) Version 5.0 of Grade ≥ 2 , such subjects should be discontinued from further dosing and, if applicable, followed for resolution.
- If a subject experiences a new onset adverse hematologic adverse event (including laboratory abnormalities) of Grade ≥ 2 , such subjects should first have laboratory abnormalities verified by repeat measure, and if repeat measure confirms the new onset abnormality, such subjects should be discontinued from further dosing, and if applicable, followed for resolution.
- If a subject experiences an adverse event Grade ≥ 3 for any organ system, such subjects should be discontinued from further dosing and, if applicable, followed for resolution.
- The study drug should be discontinued in subjects who develop evidence of hepatocellular injury that may be caused by the study drug consistent with Hy's Law. Such an adverse event should be reported as a serious adverse event (SAE).

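### Protocol 7.1.1 allows restart after Grade 2 or higher cardiovascular or hematologic events for which 7.2.1 stops dosing, and the Table 4 hemoglobin limit is in the wrong unit

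*Protocol*

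**What the plan says.** Protocol 7.1.1 (Temporary Discontinuation) covers new cardiovascular or hematologic adverse events, with laboratory findings confirmed by a repeat test, graded under CTCAE Version 5.0. Its instruction is: "then the study drug should be temporarily discontinued for that subject. Treatment may be re-initiated if the abnormality resolves within 2 weeks" counted from onset. It adds a safeguard: "Resumption of study treatment after temporary discontinuation should always be discussed with the Medical Monitor".

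Protocol 7.2.1 (Discontinuation) has three relevant bullets in its list of reasons for discontinuation:

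- New-onset cardiovascular events of Grade 2 or higher: "such subjects should be discontinued from further dosing and, if applicable, followed for resolution".
- New-onset hematologic events of Grade 2 or higher: "such subjects should first have laboratory abnormalities verified by repeat measure", and then "if repeat measure confirms the new onset abnormality, such subjects should be discontinued from further dosing, and if applicable, followed for resolution".
- Events of Grade 3 or higher: "for any organ system, such subjects should be discontinued from further dosing and, if applicable, followed for resolution".

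Table 4 in Protocol 7.2.2 lists laboratory values that require permanent withdrawal. Its hemoglobin row reads below 6.5 mg/dL. Exclusion criterion 6 in Protocol 5.2 sets the entry limit at 10 g/dL.

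**The concern.** Whether to give more drug after a cardiovascular or hematologic event is a decision about one subject's safety, and the protocol gives two answers to it. Protocol 5.0 and 8.0 rule out waivers and exemptions. If 7.2.1 governs, a restart agreed under 7.1.1 is therefore a deviation. If 7.1.1 governs, a permanent stop after a resolved Grade 2 event takes off drug a subject whom the protocol would have kept on it. The Synopsis expects about 80 sites, so different sites could apply different rules.

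Subject-level rules carry extra weight here. Protocol 9.6 provides no independent Data Monitoring Committee, and the Phase 1 experience in subjects with AD was 28 days of dosing against 112 in this trial. Table 4 is meant to be the firm limit behind those rules, and its hemoglobin row does nothing as printed.

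**Working it through.** **Step 1. Set the two rules side by side.**

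| | 7.1.1 | 7.2.1 cardiovascular | 7.2.1 hematologic |
|---|---|---|---|
| Event | New since baseline | New onset | New onset |
| Grade | 2 or higher | 2 or higher | 2 or higher |
| Laboratory findings | Confirmed by repeat | Not addressed | Confirmed by repeat |
| Action | Temporary hold | Dosing stops | Dosing stops |
| Restart | Allowed if resolved within 2 weeks of onset | None given | None given |
| Reference to the other section | None | None | None |

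The triggers match and the actions differ. Resolution also plays a different part: in 7.1.1 it is the condition for resuming, while in 7.2.1 it is what follow-up looks for after dosing has ended. The 7.2.1 bullets sit under 7.2, which deals with discontinuation and withdrawal from the study. Temporary stops have their own section, 7.1.1.

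**Step 2. Find where the conflict bites.**

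- Grade 2, not resolved within 2 weeks: the 7.1.1 clause gives no permission to restart, and 7.2.1 stops dosing. The outcomes agree.
- Grade 2, resolved within 2 weeks: 7.1.1 permits restart and 7.2.1 does not. This is the real conflict.
- Grade 3 or higher, resolved within 2 weeks: the 7.1.1 trigger, "of Grade 2 or higher, then the study drug should be temporarily discontinued for that subject", has no ceiling, so read alone it permits restart. 7.2.1 stops dosing under both its Grade 2 and its any-organ bullets.

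**Step 3. Check the hemoglobin limit.** Inputs: 6.5 mg/dL (Table 4), 10 g/dL (exclusion criterion 6), and 1 g = 1,000 mg.

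- Limit as printed: 6.5 / 1,000 = 0.0065 g/dL.
- Entry limit in the same unit: 10 × 1,000 = 10,000 mg/dL.
- Ratio: 10,000 / 6.5 = 1,538.
- Fall needed from the entry limit: 1 − 6.5/10,000 = 99.935%. No living subject reaches this.
- With the unit read as g/dL: 1 − 6.5/10 = 35%, which is reachable and matches the unit of the exclusion criterion.

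**Step 4. Scale.** The documents give no rate for these events. For each 1% of subjects affected, the SAP sample size gives 268 × 0.01 = 2.7 subjects, or 67 × 0.01 = 0.7 per arm. Protocol 2.2.2.5 reports that all Phase 1 events were mild or moderate. That makes Grade 3 events look unlikely, but it does not show that Grade 2 events will be absent.

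**The case against.** The strongest reply is that the two sections can be followed together. The 7.1.1 restart is a permission and the 7.2.1 stop is a direction, so a site that never restarts breaches neither. A staged reading, hold first and stop if unresolved, would reconcile Grade 2. At Grade 3 or higher the any-organ stop answers the question, unless a general permission is allowed to override a specific stop. Any resumption also passes through the Medical Monitor, and Protocol 8.0 sends immediate safety concerns to the Medical Monitor and the Sponsor.

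Much of this stands, and it lowers the risk. It does not settle the rule. The staged reading appears nowhere in the text, and a duty to discuss does not say what the answer should be. A site that does restart follows one section and departs from the other.

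On hemoglobin, the reply is that this is an evident unit slip that sites would probably read as g/dL. The Grade 2 and Grade 3 stops in 7.2.1 would act first, and investigators may withdraw a subject for any safety reason. This stands as to harm. The row still needs correcting, because a mandatory limit should not depend on readers repairing it, and the Grade 2 backup is itself one of the rules in conflict.

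**Conclusion.** Both errors are in the current text, and no redaction explains them. They are wrong as written and should be fixed on subject-safety grounds. The effect on the primary analysis is unquantified and probably small.

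The conclusion about restart rests on reading the 7.2.1 bullets as permanent, which their place in the list of discontinuation reasons supports. The conclusion that hemoglobin harm is limited assumes that a new hemoglobin value near 6.5 g/dL would be graded 2 or higher. The protocol does not print the CTCAE cut-points.

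A reader might infer more than the documents support:

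- That subjects are unprotected against severe anemia. They are not, given the 7.2.1 stops.
- That the any-organ Grade 3 stop cannot be checked outside cardiovascular and hematologic events, because Appendix 12 assigns a CTCAE grade only to those. Appendix 12 also rates every event as mild, moderate or severe, and 7.2.1 already names severe events as a ground for withdrawal. SAP VII.D plans CTCAE shift tables for chemistry and urinalysis as well as hematology, and SAP VII.B tabulates events leading to drug withdrawal. What remains is a mismatch of scales, which is minor.
- That 7.1.1 holds two rival recovery standards, because it later says "Resumption of investigational product may occur so long as the laboratory finding has returned to Baseline or has only mild out-of-range levels". That sentence is confined to laboratory findings, uses the same two-week clock, and reads naturally as what resolution means for them.

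One further minor gap is real: Protocol 8.2.3 points to Section 7.0 for QTc withdrawal criteria, and Section 7.0 contains none.

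**What to change.** Make one amendment, with the medical team confirming each rule.

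(a) State one rule in both 7.1.1 and 7.2.1. The default should be the stricter 7.2.1 stop: delete the 7.1.1 restart sentence for these events and refer to 7.2.1. If the medical team intends hold-and-restart, limit it to Grade 2, cross-reference it in 7.2.1, and make Grade 3 or higher a permanent stop in both sections.

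(b) Change the Table 4 hemoglobin limit to below 6.5 g/dL.

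(c) Minor: tie the any-organ Grade 3 stop to the Severe rating already recorded for every adverse event.

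(d) Minor: have the medical team supply the QTc criterion that 8.2.3 refers to. Deleting the reference should not be the default, since it is the protocol's only mention of QTc withdrawal.

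The cost is one amendment with IRB/REB/IEC approval and, where applicable, regulatory authority approval (Appendix 2), plus a letter to sites. No visits, procedures or subjects are added, and the analysis does not change. The stricter default has a price: a subject whose Grade 2 event resolves promptly loses the rest of treatment. That is why the choice belongs to the medical team.

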7.2 Subject Discontinuation/Withdrawal from the Study

Subjects have the right to withdraw from the study at any time for any reason without penalty. The Investigator also has the right to withdraw subjects from the study if he or she feels it is in the best interest of the subject or if he or she is uncooperative or noncompliant.

Should a subject decide to withdraw, all efforts will be made to complete and report the observations as thoroughly as possible, particularly the examinations outlined in the Early Termination /Discontinuation (ET/Discon) visit.

The Investigator or one of his or her staff members should contact the subject to determine as accurately as possible the primary reason for the withdrawal.

A complete final evaluation at the time of withdrawal should be made with an explanation of why the subject is withdrawing from the study. If the reason for removal of a subject is an AE or an abnormal laboratory test result, the principal specific event or test will be recorded.

If a participant withdraws from the study, he/she may request destruction of any samples taken and not tested, and the Investigator must document this in the site study records.

7.2.1 Discontinuation

Subjects who discontinue the study after the first dose will be asked, if they agree, to come for a last assessment (ET/Discon visit). Subjects who are discontinued for safety reasons may be asked to come for additional follow-up visits, at the Investigator's discretion, after the ET/Discon visit to ensure appropriate medical care and AE follow-up.

Reasons for discontinuation include the following:

- The Investigator decides that the subject should be withdrawn for any of the following reasons, but not limited to: difficulties in obtaining blood samples, violation of the protocol, severe AEs or SAEs, or for any other reason relating to the subject's safety or integrity of the study data. If this decision is made because of a SAE, the study drug is to be discontinued in that subject immediately and appropriate measures are to be taken. The Investigator will notify the Sponsor immediately.
- The attending physician requests that the subject be withdrawn from the study.
- The subject, for any reason, requires treatment with another systemic therapeutic agent that has been demonstrated to be effective for treatment of the study indication (e.g., oral corticosteroids, dupilumab, tralokinumab oral calcineurin inhibitor, oral immunosuppressive). In this case, discontinuation from the study occurs immediately upon introduction of the new agent.
- The subject is lost to follow-up. In this case, a reasonable attempt to contact the subject and ascertain his or her status must be made, and these attempts must be documented.
- The subject becomes pregnant at any time during the study.
- A clinically significant change in a laboratory parameter occurs (See [Table 4](#)),
- Onset of an opportunistic infection during the study.
- Other: the subject may withdraw from the study for any other reason, including withdrawal of consent.

- The Sponsor or regulatory authorities, for any reason, stop the study. In this case, all subjects will be discontinued from the study. The Investigator will immediately, on discontinuance of the study by the Sponsor, in its entirety or at a clinical trial site, inform both the subjects and the Institutional Review Board/Research Ethics Board/Independent Ethics Committee (IRB/REB/IEC) of the discontinuance, provide them with the reasons for the discontinuance and advise them in writing of any potential risks to the health of subjects or other persons.
- If during the course of treatment, a subject experiences a new onset cardiovascular adverse event consistent with Common Terminology Criteria for Adverse Events (CTCAE) Version 5.0 of Grade ≥ 2 , such subjects should be discontinued from further dosing and, if applicable, followed for resolution.
- If a subject experiences a new onset adverse hematologic adverse event (including laboratory abnormalities) of Grade ≥ 2 , such subjects should first have laboratory abnormalities verified by repeat measure, and if repeat measure confirms the new onset abnormality, such subjects should be discontinued from further dosing, and if applicable, followed for resolution.
- If a subject experiences an adverse event Grade ≥ 3 for any organ system, such subjects should be discontinued from further dosing and, if applicable, followed for resolution.
- The study drug should be discontinued in subjects who develop evidence of hepatocellular injury that may be caused by the study drug consistent with Hy's Law. Such an adverse event should be reported as a serious adverse event (SAE).

7.2.2 Laboratory Abnormalities

Table 4 Severe Laboratory Abnormalities Requiring Permanent Withdrawal from RPT193-02

Laboratory	Abnormality
Absolute Neutrophil Count (ANC)	<500 cells per mm ³
Absolute Lymphocyte Count (ALC)	<200 cells per mm ³
Hemoglobin	<6.5 mg/dL
Platelet count	<50,000 per mm ³
Creatinine	>3x baseline value or >3x ULN
Alanine Aminotransferase (ALT)	If abnormal baseline value, >5x baseline value for more than 2 weeks; If normal baseline value, >5x ULN for more than 2 weeks

7.2.3 Possible Case of Drug-Induced Liver Injury (DILI)

Subjects who present with evidence of hepatocellular injury that may be caused by drug ingestion consistent with Hy's Law with all of the following criteria acutely should be re-evaluated:

- ALT or aspartate aminotransferase (AST) > 3× ULN
- Total bilirubin > 2× ULN
- No signs of cholestasis (alkaline phosphatase [ALP] < 2× ULN)
- No other assignable cause such as liver metastases, pre-existing hepatic disease, viral hepatitis, alcohol abuse, ischemia, etc.

Re-evaluation should include repeat of AST, ALT, total bilirubin and alkaline phosphatase along with additional laboratory assessments including: albumin, creatine kinase, direct bilirubin, gamma-glutamyl transferase (GGT), and prothrombin time (PT)/international normalize ratio (INR). Additional medical and/or laboratory investigation to investigate other potential causes (e.g., alcohol use, infectious hepatitis) should also be considered and assessed as appropriate by the Investigator. Potential cases satisfying Hy's law should be reported as SAEs. If a subject satisfies Hy's law, study drug should be discontinued for the subject.

7.3 Lost to Follow-up

A subject will be considered lost to follow-up if he or she fails to return for scheduled visits and is unable to be contacted by the study site staff.

The following actions must be taken if a subject fails to return to the clinic for a required study visit:

- The site will attempt to contact the subject and reschedule the missed visit. The site will then counsel the subject on the importance of maintaining the assigned visit schedule and ascertain if the subject wishes to or should continue in the study.
- Before a subject is deemed lost to follow-up, the Investigator or designee will make every effort to regain contact with the subject (where possible, 3 telephone calls and, if necessary, a certified letter to the last known mailing address of the subject, or local equivalent methods). These contact attempts should be documented in the medical record or study file of the subject.

If all attempts to contact the subject fail, he or she will be considered to have withdrawn from the study with a primary reason of lost to follow-up.

8.0 STUDY ASSESSMENTS AND PROCEDURES

- Study procedures and their timing are summarized in the SoA.
- Protocol waivers or exemptions are not allowed.
- Immediate safety concerns should be discussed with the Medical Monitor and Sponsor immediately upon occurrence or awareness to determine if the subject should continue or discontinue study treatment.
- Adherence to the study design requirements, including those specified in the SoA, is essential and required for study conduct.
- All screening evaluations must be completed and reviewed to confirm that potential subjects meet all eligibility criteria. The Investigator will maintain a screening log to record details of all subjects screened and to confirm eligibility or record reasons for screening failure, as applicable.
- Procedures conducted as part of the subject's routine clinical management (e.g., blood count) and obtained before signing of the informed consent form (ICF) may be utilized for screening or baseline purposes provided the procedures met the protocol-specified criteria and were performed within the time frame defined in the SoA.
- The maximum amount of blood collected from each subject over the duration of the study, not including any extra assessments that may be required, will be specified in the ICF. Repeat or unscheduled samples may be taken for safety reasons or for technical issues with the samples.
- Demographic information related to age and ethnicity will be collected at screening.
- In addition to a detailed history of AD, medical history of other non-AD conditions should be obtained including disease duration and current medications. A smoking history should also be obtained.

8.1 Efficacy Assessments

When subjects arrive at a visit requiring efficacy assessments, subjects should begin with subject-reported assessments (i.e., itch NRS, skin pain NRS, PtGA, DLQI, subject-oriented eczema measure [POEM], ADSS, subjective portion of the SCORAD), and as applicable, the ACQ-5 and [REDACTED] before evaluation by the Investigator. After completion of these subject-reported assessments, AD efficacy assessments will then be performed in a standardized order, starting with the vIGA, followed by the BSA, followed by the EASI score, and finished by the objective portion of the SCORAD.

8.1.1 Rater Qualifications and Training

Investigator assessments of AD will only be performed by trained Investigators or sub-investigators. Raters must complete the protocol-associated training for the vIGA, BSA, EASI, and SCORAD within 6 months prior to site activation. While Investigators or sub-investigators who are board-certified dermatologists are preferred, qualified non-dermatologist physician or

licensed medical professional (e.g., Nurse Practitioner) who has previously had documented experience in such assessments in AD clinical trials may be designated by the primary site Investigator to perform such evaluations. As with other raters in the study, these raters must complete all protocol-associated training.

Every effort should be made to have the same rater perform all AD efficacy assessments for an individual subject through the course of participation in the study.

8.1.2 Subject Questionnaires and Treatment Diaries

Subject questionnaires and treatment diaries will be completed via an electronic application on their personal electronic device or via site provisioned device if they choose not to use their own. If they choose to use their own device, the site will provide clear instructions on how to download and set up the application.

Subjects will complete daily e-Diaries including compliance with study drug and all questionnaires that are required listed in SoA. The e-Diary data will be reviewed regularly for compliance and queries by the monitors and study staff. Any queries identified will be managed by IQB and the clinical site.

8.1.3 Validated Investigator Global Assessment (vIGA)

[REDACTED]

8.1.4 Body Surface Area (BSA) of AD Affected Skin

The overall BSA affected by AD will be evaluated (from 0% to 100%) at the visits specified in the SoA. The palmar surface of one hand represents ~1% of a subject's total BSA. To be eligible, subjects must have a BSA of $\geq 10\%$ at the Screening and Baseline visits.

